8.3 Dosing

Study arm A and Study arm B

Subjects will take their assigned formulation of nifedipine with 8 fl. oz. of ambient temperature water at their scheduled time point after a fast of at least 8-hours.

Study arm C and Study arm D

Subjects will take omeprazole/sodium bicarbonate capsules from Day 1 to Day 6 after a fast of at least 8 hours with 8 fl. oz. of ambient temperature water at their scheduled time point.

Also, subjects will take their assigned formulation of nifedipine together with omeprazole/sodium bicarbonate capsules on Day 7 after a fast of at least 8-hours with 8 fl. oz. of ambient temperature water at their scheduled time point.

Subjects will take their Day 1 to Day 2 doses of omeprazole/sodium bicarbonate capsules at the clinic and will be released 1 hour post-dose.

SmartPill™ Administration

Subjects will take SmartPill™ with 8 fl. oz. of water approximately 30 minutes prior to nifedipine (Study arm A and B) dosing and on Day 7 before omeprazole/sodium bicarbonate capsules and nifedipine dosing (Study arm C and D) to monitor the gastric pH. If subjects cannot swallow SmartPill™ with 8 fl. oz. of water, a maximum of 16 fl. oz. of additional water will be given to the subjects by increments of 4 fl. oz. (i.e. no more than 24 fl. oz. water in total). The total amount of water consumption will be recorded.

Immediately after ingesting a SmartPill™ capsule, subjects are fitted with the wireless Data Recorder to wear on a belt or lanyard until the SmartPill™ capsule passes with a regular bowel movement. The participant will wear the Data Recorder at all time between SmartPill™ dosing and the last pharmacokinetic sampling (i.e., 48 hrs after administering nifedipine ER tablets) in each of the Periods, except while bathing or sleeping. The recorder should be removed while bathing and placed close by where it will not get wet. While sleeping, the participant will be instructed to place the data recorder under the pillow or on a nightstand by the bed. The SmartPill™ is expected to pass within 5 days of ingestion, and participants will be asked to return the Data Recorder before being discharged.

The procedure of dosing and instructions on SmartPill™ will be described in the study directive.

For all periods (Study arms A, B, C, and D), subjects will be instructed not to touch, chew, bite or break the drug products (nifedipine, omeprazole/sodium bicarbonate, SmartPills). If a subject chews, bites or breaks any of the drug products, that subject will be removed from the study. If the subject touches nifedipine or omeprazole/sodium bicarbonate, a replacement dose will be administered. Subjects must consume the drug products and finish the water provided within a few minutes, and the actual time will be recorded.

A hand and mouth check will be conducted by clinic staff immediately following dosing.

8.4 Gastric pH

The gastric pH will be monitored through SmartPill™ Technology. The pH will be measured at 0, 1, 2, 3, 4, 5, 6, 7, and 8 hours in each study period. The pH will be monitored continuously for 24 hours post-dose.

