SmartPill™ capsules will be administered on Day 2 approximately 30 minutes before nifedipine dosing (Study arm A and B), and on Day 7 prior to dosing of nifedipine and omeprazole/sodium bicarbonate capsules (Study arm C and D).

Gastric pH Time-points	The pH will be measured at 0, 1, 2, 3, 4, 5, 6, 7, and 8 hours after SmartPill™ administration in each study arm. The pH will be monitored continuously for 24 hours post-dose.
Analyte(s) to be measured:	Plasma samples will be assayed for nifedipine using a validated analytical method according to the principles of Good Laboratory Practice.
Pharmacokinetics and Gastric pH:	Descriptive statistics of pharmacokinetic parameters AUC_t , AUC_{inf} and C_{max} , as well as T_{max} , λ and $T_{1/2}$ will be calculated for each study arm group. The descriptive statistics of the gastric pH and change of gastric pH will be calculated for both test and reference products.
Statistical Analysis:	
For Pharmacokinetic Data: Analysis of Variance (ANOVA) for ln-transformed AUC_t, AUC_{inf} and C_{max}, and untransformed T_{max}, λ and $T_{1/2}$. T_{max} will also be analyzed using an additional non-parametric test (Wilcoxon test). The 90% confidence intervals (CI) for the ratios of geometric means for AUC_t, AUC_{inf} and C_{max} will be calculated based on the least square means (LSMEANS) and ESTIMATE of the ANOVA.
 
For Pharmacodynamic Data: Analysis of Variance (ANOVA) for gastric pH and change of gastric pH from baseline will be carried out.

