The SmartPill™ motility testing system is an ingestible capsule that offers a convenient and radiation-free way to assess motility by measuring pressure, pH, and temperature throughout the entire gastrointestinal (GI) tract for patients with unexplained GI symptoms, such as nausea, bloating, constipation, abdominal pain, and vomiting. As it moves through the GI tract, it wirelessly and continuously transmits data to a recorder worn on the belt or lanyard for up to 5 days or when it passes with a regular bowel movement.

In the current study, the SmartPill™ will be used to measure subjects' gastric pH conditions (over a period of 8 hours) under which the nifedipine and co-administered nifedipine and omeprazole/sodium bicarbonate is released in vivo. This direct measurement of gastric pH will confirm a positive pharmacologic response (i.e. increased gastric pH) to proton pump inhibitors in healthy volunteers and determine the extent of gastric pH elevation as a result of 7-day multiple-dose of omeprazole/sodium bicarbonate capsules. In contrast with conventional gastric or nasogastric intubation methods, subjects should feel significantly less pain or discomfort when swallowing the capsule or while the capsule moves through the GI tract. It is naturally passed during a bowel movement, usually within a few days.

SmartPill™ uses MotiliGI® software to display and analyze the data, providing test results in both graphical and report formats. SmartPill™ provides valuable diagnostic information including:

- Gastric emptying time

- Small bowel transit time
- Colonic transit time
- Whole gut transit time
- Pressure patterns from the antrum and duodenum

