13.2 Pharmacodynamic (PD) Analysis Data Set

The data from the following subjects meeting one of the criteria will be included in the final PD and statistical analysis:

Subjects who were dosed with SmartPill™ and have collected Gastric pH samples up to 4 hours' time point in any given period.

Any decision for excluding data from the final pharmacokinetic and pharmacodynamics data set will be provided with a detailed explanation and will be properly recorded and dated.

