13.3.2 Pharmacodynamic Analysis

Pharmacodynamic (PD) parameters of omeprazole/sodium bicarbonate (i.e. proton pump inhibitors) will be evaluated for all subjects with at least 4 hours pH measurement. The PD parameters include gastric pH, change of gastric pH from baseline.

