13.3.3 Statistical Analysis

Descriptive statistics (min, max, median, mean, standard deviation and coefficient of variability) of all PK parameters will be provided for nifedipine for all study arm groups.

ANOVA including sequence, subjects nested within sequence, period and study arm will be performed on the ln-transformed data for AUC_t , AUC_{inf} and C_{max} and on the untransformed data for T_{max} , λ and $T_{1/2}$.

T_{max} will be analyzed using an additional non-parametric test (Wilcoxon test).

The 90% CI of the ratios of geometric means for AUC_t , AUC_{inf} and C_{max} will be calculated based on the LSMEANS and ESTIMATE of the ANOVA.

The following PK comparisons will be carried out:

- Test with PPI (Study arm C)/Test without PPI (Study arm A)
- Reference with PPI (Study arm D)/Reference without PPI (Study arm B)
- Test with PPI (Study arm C)/Reference with PPI (Study arm D)
- Test without PPI (Study arm A)/Reference without PPI (Study arm B)

For Pharmacodynamic Data:

The descriptive statistics (min, max, median, mean, standard deviation and coefficient of variability) of the gastric pH and change of gastric pH will be calculated for both test and reference products.

Analysis of Variance (ANOVA) for gastric pH and change of gastric pH from baseline will be carried out.

The following gastric pH comparisons will be carried out:

- Study arm C PPI (Day7) – Study arm A (Day2)

- Study arm D_{PPI (Day7)} – Study arm B_(Day2)
- The comparison of the change between test and reference can be assessed

Additional statistical and alternate tests will be performed if necessary.

Missing data will not be included in the statistical analysis. There are potential two kinds of unbalanced designs for the analysis: (1) unequal number of subjects across groups, (2) missing cells: there are not available data for some subjects. The Type 3 method will be used for the calculation of sums of squares using SAS software. All the fixed effects will be tested using the Type 3 in the ANOVA to detect statistically significant differences ($\alpha=0.05$) if applicable. A mixed effects ANOVA model for gastric pH with fixed factors of sequence, period, and study arm and random effects of subject will be fit. A compound-symmetric or other appropriate covariance structure will be used in the analysis.

The null hypotheses for gastric pH comparisons for different study arms are:

- For the comparison of Study Arm A and Study Arm C

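### SmartPill readings to 8 h count as gastric pH with no rule that the capsule is still in the stomach, which weakens the confirmation and sizing of the PPI effect

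*Combined protocol and SAP*

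**What the plan says.** The synopsis lists the gastric pH time points on a clock that starts at capsule ingestion: hourly from 0 to "7, and 8 hours after SmartPill™ administration in each study arm". Section 8.4 repeats them: "The pH will be measured at 0, 1, 2, 3, 4, 5, 6, 7, and 8 hours in each study period". It adds that pH is monitored continuously for 24 hours after dosing. Section 3.3 also takes eight hours as the gastric window. The same section says that the capsule works "by measuring pressure, pH, and temperature throughout the entire gastrointestinal (GI) tract" and lists gastric emptying time among the outputs of its software. It gives the pH data a definite job: to confirm that the PPI raised gastric pH and to determine by how much.

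For the analysis, Section 13.2 admits subjects who took the capsule and "have collected Gastric pH samples up to 4 hours". Section 13.3.2 says the PD parameters "will be evaluated for all subjects with at least 4 hours pH measurement". Section 13.3 applies the analysis to all data of the included subjects. Section 13.3.3 specifies the model: "A mixed effects ANOVA model for gastric pH with fixed factors of sequence, period, and study arm and random effects of subject will be fit". None of these sections uses gastric emptying time to decide which readings are gastric.

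**The concern.** The capsule is meant to leave the stomach; Section 10.1 treats delayed passage with the capsule still in the stomach as a complication. Once it has left, its pH readings describe the intestine in every arm and no longer show whether acid secretion is suppressed. Followed literally, the plan places these readings in the same variable as the true gastric ones.

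At stake is the reading of the PK result. If the nifedipine ratios with and without PPI turn out similar, the natural question is whether gastric pH was in fact raised, and by how much. The pH comparisons C minus A and D minus B are there to answer it. If they contain intestinal readings, they can understate the elevation and make the no-PPI arms look less acidic than they were.

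**Working it through.** The documents give no pH effect size, SD, sample size or power, so there is no stated figure to reproduce. They also give no gastric residence time, no pH under PPI and no intestinal pH. Those values below are assumptions.

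**Clock or location.** The reading times (Sections 1.0 and 8.4) are set by the clock. The entry rule (13.2, 13.3.2) is set by record length. The model (13.3.3) has sequence, period, arm and subject, with no term for hour or capsule location. The one item tied to location, gastric emptying time (3.3), appears in no analysis rule.

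**Formula for a mean over the readings.** Let G0 and G1 be gastric pH without and with PPI, and I the pH after emptying. Let pA and pC be the shares of readings taken in the stomach without and with PPI.

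- Mean without PPI = pA × G0 + (1 − pA) × I
- Mean with PPI = pC × G1 + (1 − pC) × I
- Difference = pA × (I − G0) − pC × (I − G1)

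If pA = pC = p, the difference is p × (G1 − G0), whatever the value of I. The retained fraction of the effect is then the gastric share of the readings.

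**Retained share, equal emptying in all arms.** With residence T hours, the readings at hours below T are gastric.

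| Assumed residence | Mean over 0–8 h (9 readings) | Mean over 0–4 h (5 readings) |
|---|---|---|
| 2 h | 2/9 = 22% | 2/5 = 40% |
| 3 h | 3/9 = 33% | 3/5 = 60% |
| 4 h | 4/9 = 44% | 4/5 = 80% |
| 5 h | 5/9 = 56% | 5/5 = 100% |
| past 8 h | 9/9 = 100% | 5/5 = 100% |

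**Example in pH units.** Assume G0 = 1.5, G1 = 5 and I = 6.5, so the true difference is 3.5. With 3 h residence in all arms, the 0–8 h mean gives 3/9 × 3.5 = 1.17 and the 0–4 h mean gives 3/5 × 3.5 = 2.10.

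**Unequal emptying, same pH values, 0–8 h mean** (difference = 5 × pA − 1.5 × pC):

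- 2 h without PPI, 3 h with: 1.11 − 0.50 = 0.61
- 3 h and 4 h: 1.67 − 0.67 = 1.00
- 4 h and 3 h: 2.22 − 0.50 = 1.72
- 6 h and 2 h: 3.33 − 0.33 = 3.00

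All are below 3.5. The effect is overstated only if pA > 0.7 + 0.3 × pC. For example, residence past 8 h without PPI and 2 h with PPI gives 5.00 − 0.33 = 4.67. At the other extreme, the sign reverses if pA < 0.3 × pC: 2 h without PPI and 7 h with PPI gives 1.11 − 1.17 = −0.06.

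**Other summaries, equal emptying.** The median of nine readings is the fifth in order. With 5 h residence, five readings are gastric and the median difference is the full 3.5. With 4 h or less, the median is intestinal in both arms and the difference is 0. An hour-by-hour analysis shows 3.5 at hours before emptying and 0 afterwards.

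**The case against.** The strongest reply is that the size is unknown. The plan does not say whether the nine readings are averaged, reduced to a median or analysed by hour, and the only summary named in its pH hypotheses (Section 13.3.3) is a median. A reader might infer that the PPI effect will shrink by the percentages in the table, and always toward zero. The documents do not support that: the percentages belong to a mean with assumed and equal emptying times, and the direction depends on emptying in each arm. This objection stands against any fixed figure. It does not remove the gap, because under each summary the later readings are mislabelled and the result depends on when capsules empty.

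A reader might also infer that hourly readings from one capsule are treated as independent, so that standard errors are too small. The text does not support this either. Directly after the model sentence, Section 13.3.3 commits to a compound-symmetric or other suitable covariance structure, and the random subject effect absorbs part of the correlation. What remains is only that the level of that structure, subject or subject within period, is not stated.

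Finally, Section 13.3 allows justified changes to the analysis, Section 13.2 allows documented exclusions, and Section 13.3.3 allows additional tests. These leave room for a correction and no data are lost. They do not set the rule in advance, and in an open-label study the gastric window should not be chosen after the traces have been seen.

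**Conclusion.** The gap is real: no section limits gastric pH to readings taken in the stomach, although the device supplies the time needed to do so. For a mean over 0–8 h with similar emptying across arms, 22% to 56% of the PPI difference would remain for an assumed residence of 2 to 5 hours, and all of it if residence exceeds 8 hours. Other summaries would be affected differently, and markedly unequal emptying could change the direction.

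The consequence is limited to the confirmation and sizing of the PPI response. A reader might infer that the bioequivalence or interaction results are compromised. They are not: the Section 4.1 hypotheses rest on nifedipine AUC and Cmax, and no rule makes them depend on pH. This should be fixed before the pH data are analysed, but it does not stand in the way of the PK analysis.

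**What to change.** In Sections 8.4 and 13.2 to 13.3.3:

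- Define gastric pH as readings from ingestion to each capsule's own gastric emptying time, and treat later readings as not gastric. Do not identify emptying from the pH rise alone, because that rise may be small under PPI; the device also records pressure and temperature.
- Reduce each subject-period to one pre-named summary, such as the median during gastric residence, and fit the stated model to it. Separate readings before and after the Day 7 dose, since the capsule is swallowed about 30 minutes earlier.
- Replace the 4-hour entry rule with documented gastric residence.
- Report emptying time by arm, with a sensitivity analysis for uncertain emptying times.

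The cost is analysis wording and programming on data already recorded. The downsides are that some emptying times will be uncertain, particularly under PPI, and that short residence leaves few gastric readings, with more weight on the period before the Day 7 dose.

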8.5 Safety Monitoring

In the interest of the subject safety the following safety parameters will be conducted on all subjects.

8.5.1 Vital Signs

Vital signs (BP, HR, RR and temperature) will be monitored for Study arm A and B and on Day 7 for Study arm C and D at pre-dose* and at 4, 12 and 24 hours after dosing in each study period and at pre-dose and at 1 hour after omeprazole/sodium bicarbonate capsules dosing from Day 1 to Day 6 in each study period for Study arm C and D.

Pre-Dose and Post-Dose (all periods):

Acceptable Range - systolic blood pressure between 95-140 mmHg, diastolic blood pressure between 55-90 mmHg, inclusive, and heart rate between 50-100 bpm, inclusive.

All subjects with vital signs outside of the acceptable range will have their vital signs repeated up to two times. If vitals are still outside of acceptable range, the PI/Sub-Investigator will determine appropriate course of action.

Additional vital signs measurements will be taken if deemed necessary by the PI/Sub-Investigator. Blood draws at pre-determined time (+/- 5 min) will take precedence over vital signs measurements and other scheduled activities, should a timing conflict arise unless deemed necessary by the PI/Sub-Investigator.

8.5.2 ECG

ECG measurements are not required during this study unless deemed necessary by the PI/Sub-Investigator.

8.5.3 Health Monitoring

For Study arm A and B, the PI/Sub-Investigator will be present approximately 30 minutes prior to SmartPill™ administration until at least 6 hours after the last subject is dosed with nifedipine.

For Study arm C and D, from Day 1 to Day 6, the PI/Sub-Investigator will be present from approximately 30 minutes prior to omeprazole/sodium bicarbonate capsules until at least 1 hour after dosing in each study period. On Day 7, the PI/Sub-Investigator will be present from approximately 30 minutes prior to SmartPill™ administration until at least 6 hours after the last subject is dosed with nifedipine together with omeprazole/sodium bicarbonate capsules in each study period.

*Within 12 hours prior to nifedipine administration.

The PI/Sub-Investigator will remain on-call throughout the duration of the study.

Health monitoring will be conducted throughout the study or as needed. Adverse events will be monitored throughout the study.

8.6 Post-Study Tests

Clinical laboratory tests (hematology, serum chemistry and urinalysis), as per [Appendix B – Clinical Laboratory Assessment](#), will be repeated prior to discharge at the end of the study or after withdrawal/dismissal of a subject from the study.

At exit, a symptom-directed physical exam with the possibility for a full physical exam if deemed necessary by the PI/Sub-Investigator including vital signs (BP, HR, Temperature and RR) will be conducted upon completion of the study or after withdrawal/dismissal of a subject from the study, where possible.

8.7 Sample Collection and Processing

Blood will be obtained by direct venipuncture in the arm, or via an indwelling cannula. Subjects may use up to 1 indwelling cannula in each study period. If the cannula fails to work (i.e. it becomes clogged), the remaining samples will be taken by direct venipuncture. If catheter will be used, the residual volume in the dead space will be washed with saline each time before taking the sample. Subjects who use cannulas will have them removed:

- After the last blood sample collection of confinement (not later than the 24 hour time point);
- If deemed necessary by clinic staff (for any reason);
- If subject requests removal.

Blood sample collection times will be recorded on the appropriate source documents and reported for each subject.

[figure not shown]
Number of Samples	17 samples from 17 time points in each study period
Total Volume of Blood (for all periods, including approximately 29 mL for pre- and post-study procedures and 44 mL for laboratory testing at check-in for each study period)	Approximately 345 mL of blood
Type of Vacutainer	Pre-chilled K ₂ EDTA Vacutainer®, 4 mL
Blood Sampling Time Points ♦	Pre-dose (0 hour) and at 1, 2, 3, 4, 5, 6, 7, 8, 9, 10, 12, 16, 20, 24, 36 and 48 hours after nifedipine dosing in each study period.

The blood samples collected from each subject will be processed and divided into 2 aliquots. The blood sampling and processing will be performed as per the laboratory directive.

8.8 Sample Shipment

One set of aliquots from all subjects will be shipped to the bioanalytical facility packed on dry ice. Once the initial set has been confirmed to have been received by the bioanalytical facility, the second set of aliquots will then be shipped.

All shipments will be accompanied by an inventory list and delivered to the bioanalytical facility:

Clinic personnel will notify the analytical laboratory prior to shipment by phone, fax or e-mail. The bioanalytical laboratory will notify BPSI by either e-mail or fax of confirmation of receipt of each aliquot.

♦ Pre-dose samples to be obtained within 2 hours prior to nifedipine administration.

9.0 DRUG PRODUCTS

9.1 Drug Information

Treatment Code	A (Test)	B (Reference)	PPI/antacid
Drug Name:	Nifedipine	PROCARDIA XL (nifedipine)	omeprazole/sodium bicarbonate
Strength:	60 mg	60 mg	40 mg / 1100 mg
Dosage Form:	Extended-release tablets	Extended-release tablets	Capsules
			
Dose:	1 x 60 mg	1 x 60 mg	1 x 40 mg/1100 mg (once daily for 7 consecutive days)

Device Name:	SmartPill™
Dosage Form:	Capsule (26 mm x 13 mm)
Manufactured by/for:	Given Imaging
Dose:	1 capsule 30 minutes prior to SmartPill™ administration

9.2 Labeling, Maintenance, and Retention of Study Drugs (Nifedipine, omeprazole/sodium bicarbonate, SmartPill™)

Each investigational study drug will be labeled (in English) with a statement indicating that the drug is an investigational drug to be used only by a Qualified Investigator and will include but not limited to: Drug Name, Strength, Protocol Number, Sponsor's Name and Address, the recommended storage conditions for the drug, Expiry/Retest Date (when available) and Lot/Batch Number.

